8.2. Number of Patients and Sites

Approximately 300 patients are planned to be randomized for Part A, Period 1 of the study at approximately 25 study centers.

8.3. Method of Treatment Assignment and Blinding

Part A

Period 1: Patients will be randomized such that approximately N = 130 for 12 mg BID and N = 170 for 8 mg BID) in an attempt to have approximately equal numbers of patients eligible for Part A, Period 2. Randomization will be stratified by scalp hair loss into one of the following two categories: 1) Partial scalp hair loss (SALT ≥ 50 and < 95); 2) Complete or near-complete scalp hair loss (SALT ≥ 95).

The randomization schedule will be generated prior to study start. Tablets and packaging of 8 mg and 12 mg CTP-543 will be identical in appearance.

Period 2: For each dose group, patients identified as Responders in Period 1 will be randomized in a 1:1 ratio to a dose reduction arm or a placebo (drug discontinuation) arm. For the dose reduction arm, patients previously on 12 mg BID in Period 1 will be assigned to 8 mg BID and

patients previously on 8 mg BID will be assigned to 4 mg BID. Given the previous experience with the primary endpoint for Period 1, it is expected that approximately 50 patients from each dose group in Period 1 will be Responders. Consequently, it is expected that approximately 25 patients from each dose group will be assigned to dose reduction and 25 patients will be assigned to drug discontinuation in Period 2.

The randomization schedule will be generated at the end of Period 1. Patients previously on 12 mg BID in Part A, Period 1, will receive 8 mg or placebo tablets twice daily for up to 24 weeks. Patients previously on 8 mg BID in Part A, Period 1, will receive 4 mg or placebo tablets twice daily for up to 24 weeks. Tablets and packaging for 4 mg CTP-543, 8 mg CTP-543 and placebo will be identical in appearance.

Part B

For each dose group, patients identified as having a LOM following either *dose reduction* or *drug discontinuation* in Part A, Period 2 will be assigned back to the original dose they received in Part A, Period 1. Study drug dosing regimen will be blinded by administering 2 x 8 mg tablets or 2 x 12 mg tablets twice-daily for 24 weeks. Tablets and packaging of 8 mg and 12 mg CTP-543 will be identical in appearance.

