- 23. Participation in another investigational study within the greater of 4 weeks or 5 half-lives of an investigational medication prior to screening or during the study.
- 24. Use of strong cytochrome P450 3A4 (CYP3A4) inhibitors (such as, but not limited to clarithromycin, conivaptan, grapefruit juice, indinavir, itraconazole, ketoconazole,

- lopinavir/ritonavir, mibefradil, nefazodone, nelfinavir, posaconazole, saquinavir, telaprevir, telithromycin, voriconazole, or fluconazole) dosed for systemic exposure.
- 25. Use of strong CYP3A4 inducers (such as, but not limited to barbiturates, carbamazepine, efavirenz, glucocorticoids, modafinil, nevirapine, oxcarbazepine, phenobarbital, phenytoin, pioglitazone, rifabutin, rifampin, St. John's Wort, or troglitazone) dosed for systemic exposure.
- 26. Donation of blood > 499 mL of blood or plasma within 56 days of Screening (during a clinical trial or at a blood bank donation) and for 30 days after last dose of study drug.
- 27. Clinically significant medical condition, psychiatric disease, or social condition, as determined by the Investigator, that may unfavorably alter the risk-benefit of study participation, adversely affect study compliance, or confound interpretation of study results.

Investigational product, dosage and mode of administration:

CTP-543 will be dosed orally as tablets at doses of 8 mg, 12 mg, or 4 mg every 12 hours.

Reference therapy, dosage and mode of administration:

Matching placebo will be dosed orally as tablets every 12 hours during Part A, Period 2.

Duration of treatment:

Part A, Period 1: Patients will receive study drug for 24 weeks in the Treatment Period.

Part A, Period 2: Responders from Part A, Period 1 will receive up to 24 weeks of additional treatment with active or placebo.

Part B: Patients will be treated with active drug for 24 weeks.

Patients will be dosed in the study with CTP-543 up to a total of 72 weeks.

Duration of study participation:

Patients will participate in the study for up to approximately 80 weeks if exiting the study after the 4-week Safety Follow-up (4-week Screening, 48-week Treatment Part A, 24-week Treatment Part B, 4 week Safety Follow-up). Upon completion of the 24-week Treatment Period, patients will be eligible to either complete treatment and exit the study following the 4-week Safety Follow-up visit, or enroll into an open-label extension study.

Criteria for evaluation:

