Patients in Part A, Period 2 will stay on their assigned dose for a maximum of 24 weeks or until they meet the criteria for loss of regrowth maintenance (LOM), defined as an absolute SALT score >20. Any patient meeting the LOM criteria at any assessment timepoint during Part A, Period 2 will enter Part B of the study and return to their original CTP-543 treatment from Part A, Period 1 (8 mg BID or 12 mg BID). Patients not meeting the LOM criteria (e.g., their absolute SALT score remains \leq 20) at the end of 24 weeks will have the opportunity to continue receiving treatment in the Open-Label Extension study (CP543.5001) or they will complete treatment at Week 24 and return in 4 weeks for the Post-Treatment Safety Follow-up.

Assessment of treatment response using SALT for efficacy will occur at 4, 8, 12, 16, 20 and 24 weeks. The primary efficacy analysis will be conducted when all patients have completed Week 24 of Part A, Period 2. The study design is depicted below.

Part A: Treatment and Dose Modification Phase

Part B: Re-Treatment Phase

Part B: Re-

Figure 2: CP543.2004 Study Design

LOM: Loss of Maintenance

Part B (Re-Treatment Phase)

Any patient from Part A, Period 2 meeting the LOM criteria (SALT > 20) will enter into Part B of the study and return to their original 8 mg BID or 12 mg BID dose assigned in Part A, Period 1. Patients will stay on their assigned dose for 24 weeks regardless of whether they meet the criteria for Restoration of Regrowth (ROR) or not. ROR is defined as the patient's attainment of an absolute SALT score ≤20. Assessment of treatment response using SALT for efficacy will occur monthly during the 24-week period. Patients will have the opportunity to continue receiving treatment in the Open-Label Extension study (CP543.5001) or they will complete treatment at Week 24 and return in 4 weeks for the Post-Treatment Safety Follow-up.

Safety

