scalp hair represented treatment success. Adult and adolescent AA patients participating in the study perceived that, short of 100% scalp hair, the presence of \sim 70-90% scalp hair (median 80%) represented treatment success. Nearly all queried clinicians and patients in this study agreed that for patients with \geq 50% scalp hair loss, successful treatment would be hair regrowth resulting in \leq 20% scalp hair loss.

Therefore, based on the efficacy and safety data observed in the CP543.2001, CP543.2002, and CP543.2003 studies, 8 mg BID and 12 mg BID of CTP-543 will be assessed further for efficacy and safety in this study in patients with moderate to severe alopecia areata. This study will employ SALT as the hair loss assessment tool and the criteria for definition of a responder will be the achievement of an absolute SALT score \leq 20 at Week 24, as this represents a clinically-meaningful treatment success for patients with AA.

For Part A, Period 1 the primary efficacy endpoint will be the proportion of patients who achieve an absolute SALT score of ≤20 at Week 24. This endpoint was chosen based on the data obtained from Study CP543.2001. Choosing this endpoint for Part A, Period 1 will yield an adequate number of patients moving onto the dose modification phase of the study.

For Part A, Period 2 the primary analysis is the proportion of patients who maintain an absolute SALT score of ≤20 at Week 24 following either dose reduction or drug discontinuation. Patients in Part A, Period 2 will stay on the assigned dose for a maximum of 24 weeks or until they meet the criteria for LOM. The criteria for LOM is an absolute SALT score >20. This criteria will reflect a clear loss of maintenance of the hair regrown in Period 1 but without a major loss of hair which would be emotionally disturbing to the patient.

For Part B the primary analysis is the proportion of subjects who achieve an absolute SALT score of ≤20 at Week 24 after re-treatment. Any patient from Part A, Period 2 meeting the LOM criteria will enter into Part B of the study and return to their original 8 mg BID or 12 mg BID dose from Part A, Period 1. Patients will stay on their assigned dose for 24 weeks.

Table 1: Schedule of Assessments: Part A

	Screening	Part A, Period 1					Part A, Period 2				Safety Follow-Up ⁶		

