10. DESCRIPTION OF STUDY TREATMENTS

10.1. Description of Treatments

Part A

Period 1. Patients will be stratified by extent of scalp hair loss with approximately 170 patients initially randomized to the 8 mg BID CTP-543 dose and approximately 130 patients initially randomized to the 12 mg BID CTP-543 dose.

Period 2. Eligible patients for Period 2 will be to randomized to a lower dose or placebo in a 1:1 ratio. Specifically, patients previously on 8 mg BID will be randomized to 4 mg BID or placebo. Patients previously on 12 mg BID will be randomized to 8 mg BID or placebo.

Part B

Eligible patients for Part B will be assigned to the dose they previously took in Part A, Period 1. Consequently, patients will receive either 8 mg BID or 12 mg BID for the remainder of their participation in the study.

For all study phase, patients will take the first dose of study drug in the clinic on Day 1 of the Treatment Period and will be instructed to take study drug approximately every 12 hours (\pm 3 hours) without regard to food for the duration of the study Phases.

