10.4.3. Study Drug Preparation and Administration

No study drug preparation is required. Patients will take the first dose of study drug in the clinic on Day 1 and will be instructed to take study drug approximately every 12 hours for the duration of the Treatment Period. If patients should dose study drug in the clinic on Study Visit Days dosing should be after clinical laboratory blood draws are completed.

Study drug should be taken at approximately the same times each day, with water, and without regard to food. Patients should be instructed to take one tablet in the morning and one tablet in the evening, approximately 12 hours apart. If a dose is missed, the patient should skip the missed dose and resume dosing at the next scheduled dose. The patient should not take two doses at the same time. Deviations from prescribed dosing should be discussed at each visit for assessment of compliance and retraining when necessary.

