### Part B:

For Part B of the study, the primary efficacy endpoint is the percentage of patients by dose group achieving ROR, defined as an absolute SALT score of  $\leq 20$  at Week 24 of re-treatment. The following treatment sequences will be compared:

- Dose reduction in Period 2
  - 12 mg BID reduced to 8 mg BID increased to 12 mg BID
  - 8 mg BID reduced to 4 mg BID increased to 8 mg BID

- Drug discontinuation in Period 2
  - 12 mg BID to placebo to 12 mg BID
  - 8 mg BID to placebo to 8 mg BID

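### Protocol 8.3 and SAP 7.2 state the Part B regimen as two tablets twice daily, double the 8 mg BID or 12 mg BID given everywhere else

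*Protocol*

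**What the plan says.** Protocol 8.3 describes Part B in two consecutive sentences that disagree. The first says that patients with loss of maintenance are "assigned back to the original dose they received in Part A, Period 1". The second says that the regimen is blinded by "administering 2 x 8 mg tablets or 2 x 12 mg tablets twice-daily for 24 weeks". SAP 7.2 carries the same paragraph.

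The other statements of the Part B dose agree with the first sentence:

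- Protocol 8.1 (and likewise the Synopsis and SAP 3): patients "return to their original 8 mg BID or 12 mg BID dose assigned in Part A, Period 1".
- Protocol 8.4 (and likewise footnote 8 of Table 2): patients "return to their original 8 mg BID or 12 mg BID dose from Part A, Period 1".
- Protocol 10.1, the treatment description: "patients will receive either 8 mg BID or 12 mg BID for the remainder of their participation in the study".
- SAP 8.2, one of the Part B sequences: "12 mg BID reduced to 8 mg BID increased to 12 mg BID". The Part B column headings in SAP 4 follow the same pattern.

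The Synopsis also gives the study-wide doses: "CTP-543 will be dosed orally as tablets at doses of 8 mg, 12 mg, or 4 mg every 12 hours".

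On tablet-taking, Protocol 10.4.3 says: "Patients should be instructed to take one tablet in the morning and one tablet in the evening, approximately 12 hours apart". Protocol 10.4.2 supplies one 60-count bottle at each 4-week visit. SAP 7.3 uses a factor of two tablets per day for every dose group.

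**The concern.** The section that governs Part B assignment and blinding states a dose that is wrong by a factor of two, and the error has been carried into the SAP. Someone who reads only that sentence, in either document, comes away with the wrong regimen.

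The stake is safety wording, not inference. CTP-543 is a JAK inhibitor with haematologic dose-interruption thresholds (Protocol 10.2.1). Protocol 5.4.1 describes repeat dosing up to 32 mg/day, for 7 days in healthy subjects; 48 mg appears there only as a single dose. Taken literally, the sentence would give the 8 mg group 32 mg/day and the 12 mg group 48 mg/day, in patients, for 24 weeks.

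**Working it through.** **Inputs**

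- Tablet strengths: 4, 8 and 12 mg (Protocol Table 5).
- Tablets per administration: 2 as written in 8.3; 1 in 10.4.3. Administrations per day: 2.
- Part B duration: 24 weeks = 168 days.
- Part B dispensing visits (Protocol Table 2): Day 1 and Weeks 4, 8, 12, 16 and 20, so 6.
- Bottle size: 60 tablets per 4-week visit (Protocol 10.4.2).

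**Daily dose** = tablets per administration × strength × 2

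| Group | As written in 8.3 | One tablet BID | Ratio |
|---|---|---|---|
| 8 mg | 2 × 8 × 2 = 32 mg/day | 1 × 8 × 2 = 16 mg/day | 2.0 |
| 12 mg | 2 × 12 × 2 = 48 mg/day | 1 × 12 × 2 = 24 mg/day | 2.0 |

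Only the one-tablet column reproduces 8 mg BID and 12 mg BID.

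**Supply**

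- Scheduled supply: 6 × 60 = 360 tablets.
- One tablet BID: 2 × 168 = 336 tablets, or 56 per 28 days. A bottle lasts 60/2 = 30 days, so the supply fits.
- As written: 4 × 168 = 672 tablets, or 112 per 28 days. A bottle lasts 60/4 = 15 days, and 672/60 = 11.2 means 12 bottles against 6 scheduled.

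**SAP compliance denominator**

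SAP 7.3 sets expected tablets at 2 per day. Full adherence scores 336/336 = 100% on one tablet BID and 672/336 = 200% on the literal text. The SAP's own formula therefore assumes one tablet BID.

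**Could the sentence be right on another reading?**

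- Two half-strength tablets: no. The sentence names 8 mg and 12 mg tablets, and both are listed strengths.
- One active tablet plus a dummy: no. The sentence names both tablets as active, and the Synopsis lists placebo only for Part A, Period 2.
- A planned escalation: no. The preceding sentence restores the original dose, and Protocol 10.2 allows only interruption or discontinuation for intolerability.
- Two tablets per day in total: this may be what the author meant, but it is a guess, and the text does not say it.

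**The case against.** The best reply is that this is a minor slip which the documents already correct. The disputed clause describes how the blind is kept. Protocol 10.1 defines the treatment, 10.4.3 sets the tablet-taking, and 10.4 sends sites to the Pharmacy Manual for dispensing. The manual is not available here, so confusion at sites cannot be shown. Protocol 10.3 already requires a tablet count and a compliance interview at each scheduled visit. All of this stands, and it limits the point to a wording correction. It does not make the sentence right, and the agreement elsewhere is what makes the correction certain.

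Three stronger readings are tempting, and the documents support none of them:

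- *Part B patients were, or will be, double-dosed.* Nothing shows this, and the scheduled supply could not sustain it.
- *The SAP wording overrides the protocol dose.* The primacy clause in SAP 2 concerns differences between analyses, not treatment.
- *Compliance thresholds should be used to hunt for double dosing.* SAP 7.3 computes compliance per Part/Period. With six bottles and a final visit at day 168 ± 2, it cannot exceed 360/(2 × 166) = 108% to 360/(2 × 170) = 106%. A patient who doubled the dose and emptied each bottle by day 15 would score 360/336 = 107%. So would a correctly dosed patient who returned none of the 24 spare tablets. Such a threshold would not detect the pattern most likely under one bottle per visit.

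**Conclusion.** The sentence in Protocol 8.3 and SAP 7.2 is wrong as written, by a factor of exactly two: 32 or 48 mg/day against 16 or 24 mg/day. One tablet BID is the intended regimen. This rests on the explicit Part B dose statements and the one-tablet instruction; the supply and the compliance denominator agree with them. The supply arithmetic assumes a full 168 days and one bottle at each of the six dispensing visits. It shows that the literal reading is implausible and does not measure risk.

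The point is worth fixing because it is a dose figure in an operative section. Its reach is small: no endpoint, sample size or analysis depends on it, and actual double dosing is unlikely.

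**What to change.** In Protocol 8.3 and SAP 7.2, replace the tablet description with: *one 8 mg tablet or one 12 mg tablet twice daily for 24 weeks*. Send sites a short clarification that Part B is one tablet BID.

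Leave Protocol 10.1, 10.4.2 and 10.4.3 and the factor of two in SAP 7.3 as they are; they are correct. No added audit is needed. The tablet counts and interviews under Protocol 10.3 are enough, together with the planned Part B outputs on exposure, compliance and dosing exceptions (Table 14.1.7.3; Listings 16.2.5.1.2, 16.2.5.2.2 and 16.2.5.3.2).

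The cost is one sentence in each of two documents and one site notice, with no extra patients, visits, procedures or outputs.

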8.4. Rationale for Study Design, Doses, and Primary Endpoint

Double-blind, randomized, placebo-controlled studies are considered optimal for obtaining unbiased estimates of the efficacy and safety of investigational products. The Severity of Alopecia Tool (SALT) (Olsen, 2004) was introduced as part of investigative guidelines published by the National Alopecia Areata Foundation is widely used to assess the extent of the scalp surface hair loss in AA. The SALT has been used as the hair loss measurement scale in all the studies of CTP-543 in patients with alopecia areata to date. The 24-week duration of the Treatment Period has been shown to be sufficient in establishing hair regrowth with CTP-543 and to significantly differentiate active doses from placebo as well as differentiate between doses of CTP-543.

The selection of the 8 mg and 12 mg BID doses of CTP-543 for this study is supported by the efficacy and safety of CTP-543 observed in the completed and analyzed Phase 2 CP543.2001, CP543.2002, and CP543.2003 studies. Analysis of the primary efficacy endpoint in CP543.2001 showed that the proportions of responders (patients achieving at least a 50% relative reduction in SALT score from Baseline at Week 24) were significantly greater in the 8 mg BID group and 12 mg BID group compared with the placebo group (P < 0.001 for both) and compared with the 4 mg BID group (P = 0.030 and P = 0.003, respectively). For the analysis performed on the efficacy population, 9.3% of patients in the placebo group and 21.4% of patients in the 4 mg BID group were responders, compared with 47.4% in the 8 mg BID group and 58.3% in the 12 mg BID group. Results also showed a significantly greater proportion of responders in the 8 mg BID and 12 mg BID groups which had at least 50%, 75%, and 90% relative reduction in SALT score by Week 24 compared with both the placebo group and the 4 mg BID group.

Additionally, both the 8 mg BID group and the 12 mg BID group had significantly greater proportions of patients who achieved an absolute SALT score ≤20 at Week 24 compared with the placebo group. Achieving a SALT score ≤ 20 has been reported by AA patients and clinicians to represent clinically-meaningful treatment success for AA (Wyrwich, 2020). In the Wyrwich study, qualitative interviews were conducted in the US with hair expert dermatologists and AA patients who had experienced ≥50% scalp hair loss. The clinicians judged that 80%

scalp hair represented treatment success. Adult and adolescent AA patients participating in the study perceived that, short of 100% scalp hair, the presence of \sim 70-90% scalp hair (median 80%) represented treatment success. Nearly all queried clinicians and patients in this study agreed that for patients with \geq 50% scalp hair loss, successful treatment would be hair regrowth resulting in \leq 20% scalp hair loss.

Therefore, based on the efficacy and safety data observed in the CP543.2001, CP543.2002, and CP543.2003 studies, 8 mg BID and 12 mg BID of CTP-543 will be assessed further for efficacy and safety in this study in patients with moderate to severe alopecia areata. This study will employ SALT as the hair loss assessment tool and the criteria for definition of a responder will be the achievement of an absolute SALT score \leq 20 at Week 24, as this represents a clinically-meaningful treatment success for patients with AA.

For Part A, Period 1 the primary efficacy endpoint will be the proportion of patients who achieve an absolute SALT score of ≤20 at Week 24. This endpoint was chosen based on the data obtained from Study CP543.2001. Choosing this endpoint for Part A, Period 1 will yield an adequate number of patients moving onto the dose modification phase of the study.

For Part A, Period 2 the primary analysis is the proportion of patients who maintain an absolute SALT score of ≤20 at Week 24 following either dose reduction or drug discontinuation. Patients in Part A, Period 2 will stay on the assigned dose for a maximum of 24 weeks or until they meet the criteria for LOM. The criteria for LOM is an absolute SALT score >20. This criteria will reflect a clear loss of maintenance of the hair regrown in Period 1 but without a major loss of hair which would be emotionally disturbing to the patient.

For Part B the primary analysis is the proportion of subjects who achieve an absolute SALT score of ≤20 at Week 24 after re-treatment. Any patient from Part A, Period 2 meeting the LOM criteria will enter into Part B of the study and return to their original 8 mg BID or 12 mg BID dose from Part A, Period 1. Patients will stay on their assigned dose for 24 weeks.

Table 1: Schedule of Assessments: Part A

	Screening	Part A, Period 1					Part A, Period 2				Safety Follow-Up ⁶		
Event	Day -28 to Day -1 (Visit 1)	Randomization ^{1, 2} Day 1 (Visit 2)	Week 2 (Visit 3)	Week 4, 8 (Visit 4, 5)	Week 12 (Visit 6)	Week 16, 20 (Visit 7, 8)	Week 243,4 (Visit 9)	Week 28 ⁵ (Visit 10)	Week 32 (Visit 11)	Week 36 (Visit 12)	Week 40, 44 (Visit 13, 14)	Week 484 (Visit 15)	Safety Follow-Up Visit
Informed consent	X												
Eligibility assessment	X	X											
Demographics	X												
Medical history	X	X											
Randomization		X					X^7						
PE	X	X					X					Х	X
Brief PE				X	X	X			X	X	Х		
Height	X												
Weight	X	X		X	X	X	X		X	X	X	X	X
Pregnancy test ⁸	X	X ⁹		X	X	X	X	X	X	X	X	X	
Tuberculosis test	X												
Clinical laboratory testing ¹⁰ , 11	X ¹²	X	X	X	X	X	X	X	X	X	X	X	X
Lipid assessment ¹³		X			X		X			X		X	X
HBV and HCV test	Х												
12-lead electrocardiogram	Х	X			Х		X			X		Х	X
Vital signs	X	X		X	X	X	X		X	X	Х	X	X
SALT assessment	Х	X		X	X	X	X	X^{14}	X^{14}	X^{14}	X14	Х	
Photographs	X	X		X	X	X	X	X	X	X	Х	X	
SPRO and QPRO		X			X	X	X						
CGI-S and PGI-S		X			Х	X	X						
CGI-I and PGI-I					X	X	X						
Dispense study drug		X		X	X	X	X^7	X^{15}	X^{15}	X^{15}	X15		
Pharmacokinetic blood sampling ¹⁶		X			X		X						
Study drug accountability				X	X	X	X		X	X	X	X	_
Adverse events	X				X					X			X
Concomitant medications	X		X			X				X			

PE = Physical Examination; HBV= hepatitis B virus; HCV = hepatitis C virus; SPRO = Satisfaction of Hair Patient Reported Outcome; QPRO = Quality of Hair Patient Reported Outcome; CGI-S = Clinical Global Impression of Severity; CGI-I = Clinical Global Impression of Improvement; PGI-S= Patient Global Impression of Improvement; PGI-I = Patient Global Impression of Improvement;

- ¹ Day 1 (Visit 2) may occur any time after Screening laboratory results are available and reviewed by the Investigator.
- ² For Part A, Period 1, all subsequent visits and week increments should be based on the date of Visit 2. All visit windows are ± 2 days.
- ³ Week 24 from Part A, Period 1 will also serve as the Day 1 visit for Part A, Period 2 for those who meet criteria to continue into the Dose Modification Phase.
- ⁴ Also serves as the Early Termination Visit for patient withdrawal in this period.
- ⁵ For Part A, Period 2, all subsequent visits and week increments should be based on the date of Week 24 (Visit 9). All visit windows are ±2 days.

- The Safety Follow-Up Visit is intended as an Exit Visit for those subjects who discontinue the trial or for those who do not continue into the Open-label Extension study following completion of Part A, Period 1 or Part A, Period 2.
- ⁷Randomization and dispensation of study drug will occur on Week 24 only for those subjects who meet criteria and will continue into Part A, Period 2.
- ³ Serum pregnancy test for females of childbearing potential only. Subjects who are surgically sterile or (hysterectomy or bilateral ligation) or post-menopausal (cessation of menses for at least 12 months prior to screening) need not be tested.
- Urine pregnancy test should be performed at the randomization visit.
- ¹⁰ Includes hematology and serum chemistry, fasted.
- ¹¹ Collect pre-dose if subject is dosing in the clinic on study visit days.
- ¹² Will include thyroid stimulating hormone and hemoglobin A1c at Screening only.
- ¹³ Includes total cholesterol, low-density lipoprotein, high-density lipoprotein, and triglycerides under fasted conditions.
- ¹⁴ If SALT score >20 at any visit in Part A, Period 2, patient will enter into Part B of the study and return to their original 8 mg BID or 12 mg BID dose from Part A, Period 1. However, all safety assessments outlined in Part A, Period 2 should be performed prior to dispensing study drug in Part B.
- ¹⁵ Dispensation in Part A, Period 2 will only occur for subjects whose SALT remains \leq 20. If SALT >20, the subject should proceed to Day 1 (Visit B1).
- ¹⁶ Day 1 (post-dose) and Weeks 12 and 24 (variable times post-dose)

Table 2: Schedule of Assessments: Part B

Event	Treatment Period									
Event	Day 1 ^{1, 2} (Visit B1)	Week 2 (Visit B2)	Week 4, 8 (Visit B3, B4)	Week 12 (Visit B5)	Week 16, 20 (Visit B6, B7)	Week 24 ³ (Visit B8)	Week 28 (Visit B-SFU)			
Physical examination						X	X			
Brief physical examination			X	X	X					
Weight			X	X	X	X	X			
Pregnancy test ⁵			X	X	X	X				
Clinical laboratory testing ⁶		X	X	X	X	X	X			
Lipid assessment ⁷				X		X	X			
12-lead electrocardiogram				X		X	X			
Vital signs			X	X	X	X	X			
SALT assessment			X	X	X	X				
Photographs			X	X	X	X				
Dispense study drug	X8		X	X	X					
Study drug accountability			X	X	X	X				
Adverse events	X									
Concomitant medications				X			X			

All subsequent visits and week increments should be based on the date of Visit B1. All visit windows are ±2 days.

² As Day 1 occurs on the same day as the last visit from Part A, Period 2, eligible subjects for Part B will not have assessments repeated.

³ Also serves as the Early Termination Visit for patient withdrawal in this period or any patient meeting ROR criteria and entering OLE.

⁴ The Safety Follow-Up Visit is intended as an Exit Visit for those patients who do not roll over into an open-label extension and for patients who have been discontinued from the study and completed the Early Termination Visit (Week 24).

⁵ Serum pregnancy test for females of childbearing potential only. Subjects who are surgically sterile or (hysterectomy or bilateral ligation) or post-menopausal (cessation of menses for at least 12 months prior to screening) need not be tested.

⁶ Includes hematology and serum chemistry, fasted.

Includes total cholesterol, low-density lipoprotein, high-density lipoprotein, and triglycerides under fasted conditions.

⁸ Any patient from Part A, Period 2 meeting the LOM criteria will enter into Part B of the study and return to their original 8 mg BID or 12 mg BID dose from Part A, Period 1.

